4.2 Definition of Terms

Inflammatory bowel disease (IBD) - a group of chronic, often relapsing, immunologically-mediated gastrointestinal disorders: Crohn's disease (CD) and ulcerative colitis (UC). Crohn's disease may involve any portion of the length of the gastrointestinal tract from mouth to anus in a transmural fashion from mucosa to serosa whereas ulcerative colitis primarily affects colonic mucosa and submucosa.

IBD flare - a flare of symptoms in a patient with established CD/UC who is in clinical remission, either spontaneously or after medical treatment. Relapse should be preferably confirmed by laboratory parameters, endoscopy or imaging in clinical practice. The definition of IBD flare (including severity) will be in accordance with Clinical recommendations of the Russian gastroenterological association and association of coloproctologists of Russia on the diagnosis and treatment of ulcerative colitis and Crohn's disease; Clinical Protocols of diagnosis and treatment of ulcerative colitis and Crohn's disease in the Republic of Kazakhstan and Clinical Protocol "Diagnosis and treatment of patients with diseases of the digestive system", Appendix 3 in the Republic of Belarus and local routine practice [6-10].

IBD is a chronic condition that is characterized by intermittent periods of active disease (relapses) and little or no disease activity (remission). The duration and severity of the active period vary widely from person to person. The goal of treatment of IBD is to induce and maintain remission for better outcomes of the disease.

IBD remission – a resolution of symptoms (clinical remission) and mucosal inflammation (endoscopic remission). The definition of IBD remission will be in accordance with Clinical recommendations of the Russian gastroenterological association and association of coloproctologists of Russia on the diagnosis and treatment of ulcerative colitis and Crohn's disease; Clinical Protocols of diagnosis and treatment of ulcerative colitis and Crohn's disease in the Republic of Kazakhstan and Clinical Protocol "Diagnosis and treatment of patients with diseases of the digestive system", Appendix 3 in the Republic of Belarus and local routine practice [6-10].

Biologics dose escalation will include any increase in dose, frequency, or both;

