12.6 Treatments to be documented in the study

12.6.1 IBD treatment

Due to non-interventional design of the study, the decision about particular IBD treatment strategy to the patient is taken by treating physician. All IBD medications are not provided by Sponsor.

Following medications for IBD treatment should be registered in eCRF; 5-ASA, immunosuppressive agents (including azathioprine (AZA), 6-mercaptopurine (6-MP), methotrexate (MTX), cyclosporine A), corticosteroids and biologics.

The following data should be documented for steroids:

- INN name;
- release form;
- Route of administration
- Indication
- start date;
- initial and maximum daily dose;
- funding source;
- dose, if continued / end date and the reason for modification/ discontinuation, if discontinued.

The following data should be documented for 5-ASA, immunosuppressive agents:

- INN name;
- release form;
- Route of administration
- Indication start date;
- daily dose;
- funding source;
- continued / end date and the reason for modification/discontinuation.

The following data should be documented for biologics:

- trade and INN name;
- Indication start date;
- treatment regimen (induction or supportive care);
- dosage regimen;
- Route of administration
- funding source;
- continued / end date and the reason for modification/discontinuation.

If a physician takes a decision to change something from the above it must be documented in the eCRF.

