## 6 MAIN ASSESSMENTS

### 6.1 Endpoints (outcomes)

**Primary endpoint (outcome):** Distribution of treatment patterns used in patients with moderate to severe UC and with moderate to severe CD treated with biologics. Treatment patterns will be evaluated within 2 years before enrolment – retrospective data and one year after enrolment – prospective data and will include:

- trade and INN name;
- original medication or biosimilar medication;
- dosage regimen (dose, route and frequency);
- duration of each dose regimen;
- presence of treatment modifications/discontinuation;
- funding source;
- reason(s) for modification/discontinuation of IBD medicine treatment;

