#### 8.1.2 Assessment of primary endpoint

Treatment combinations will be described for UC and CD separately based on the following criteria:

- 1) Various types of biological and non-biological treatments including the following treatment combinations:
  - a. Steroid monotherapy (by class)
  - b. Steroids (by class) + immunosuppressive therapy (by class) combinations
  - c. Immunosuppressive monotherapy (by class)
  - d. Immunosuppressive (by class) + 5-aminosalicylic acid derivatives (by class)
  - e. 5-aminosalicylic acid derivatives monotherapy (by class)
  - f. TNF-alpha inhibitor monotherapy (by trade name)
  - g. TNF-alpha inhibitor therapy (by trade name) + steroids (by class)
  - h. TNF-alpha inhibitor therapy (by trade name) + immunosuppressive therapy (by class)
  - i. TNF-alpha inhibitor therapy (by trade name) + immunosuppressive therapy (by class) + steroids (by class)
  - j. Vedolizumab monotherapy (by INN)
  - k. Vedolizumab therapy (by INN) + immunosuppressive therapy (by class)
  - l. Vedolizumab therapy (by INN) + steroids (by class)
  - m. Vedolizumab therapy (by INN) + immunosuppressive therapy (by class) + steroids (by class)
  - n. Janus kinase (JAK) inhibitor monotherapy (by trade name)
  - o. JAK inhibitor therapy (by trade name) + steroids (by class)
  - p. JAK inhibitor therapy (by trade name) + immunosuppressive therapy (by class)
  - q. JAK inhibitor therapy (by trade name) + immunosuppressive therapy (by class) + steroids (by class)

---

 Steroids will be standardized through the calculation of prednisolone equivalent dose to facilitate comparisons between the classes

Protocol ID	MACS-2017-102279	STATISTICAL ANALYSIS PLAN	Page 24 of 41	
IP	N/A		Date	30.12.2021
ID	MACS-2017-102279_SAP		Version	v1.2 final

**Disclaimer:** due to the observational nature of the study, it is impossible to predict the distribution of treatment patterns before the actual analysis is performed. The list above can be modified based on the actual study data by excluding of certain combinations (absent in the database or identified in less than 25 subjects) or by including the combinations that were not initially planned but were identified in the actual study database.

Treatment pattern will include unique combination of certain treatments or treatment combinations along with their change over time.

Each treatment combination will be analyzed using the following summary data:

- Average course duration;

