- Average maximum dose for each component of the combination (across all courses);
- Average number of courses per patient;
- Total duration of use of each combination / course for the total duration of observation (retro- and prospective);
- Distribution of each pattern by subgroups: age, gender, region, duration of the disease, disease activity (according to Visit 1 Mayo / Harvey-Bradshaw indices).

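### SAP 8.1.2 summarises biologic dosing only by an undefined average maximum dose, which does not show the frequency and duration of each dose regimen that SAP 6.1 puts in the primary endpoint

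*SAP*

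**What the plan says.** SAP 6.1 defines the primary endpoint as the distribution of treatment patterns in patients on biologics, over two retrospective years and one prospective year. Its components include "dosage regimen (dose, route and frequency"), "duration of each dose regimen" and "presence of treatment modifications/discontinuation".

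SAP 8.1.2 sets out how that endpoint is analysed. For each treatment combination it lists course duration, number of courses, total time on the combination, distribution by subgroup, and one dosing statistic: "Average maximum dose for each component of the combination (across all courses"). It does not say whether dose means per administration, per day or per interval. Dose standardisation is stated for steroids only: "Steroids will be standardized through the calculation of prednisolone equivalent dose to facilitate comparisons between the classes".

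Protocol 12.6.1 asks for "initial and maximum daily dose" for steroids only. For biologics it asks for the dosage regimen and, as a separate field, "treatment regimen (induction or supportive care"). Protocol 4.2 states: "Biologics dose escalation will include any increase in dose, frequency, or both".

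**The concern.** A maximum daily dose suits a drug that is taken daily and tapered, and the eCRF collects it for steroids. A biologic regimen is described by a dose and an interval, and the protocol itself separates an induction phase from supportive care. A single maximum across all courses carries neither the interval nor the phase.

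Two things are at stake. First, the primary analysis text does not deliver the frequency and regimen-duration components that SAP 6.1 promises. Second, the one dosing figure it does deliver may be hard to interpret. It may not respond to interval shortening, and it may differ between columns because of when patients started the drug, even if they are maintained on the same regimen.

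**Working it through.** The plan gives no figure for dosing, so there is none to reproduce on this point. Its only design figure, ±5.8% for a failure proportion of 50%, does reproduce: n = 2000 × 0.40 × 0.40 × 0.90 = 288, and 1.96 × √(0.25/288) = 5.77%. Nothing below depends on it.

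**Step 1: endpoint against analysis.** This step needs no assumption about any drug.

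| Component in SAP 6.1 | Summary in SAP 8.1.2 |
|---|---|
| Dose | Average maximum, undefined |
| Frequency | None stated |
| Duration of each dose regimen | None; durations are per course or combination |
| Induction or supportive care (collected under protocol 12.6.1) | Not used |

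**Step 2: interval shortening, reading the statistic as dose per administration.** A patient on dose D every T weeks moves to D every T/2 weeks. The maximum dose is D before and after. Dose per week goes from D/T to 2D/T, an increase of 100%. If a share f of patients on the drug does this, mean dose per unit time after the change is 1 + f times the starting value, while the average maximum stays at 1.00.

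| f (illustrative) | 0% | 10% | 20% | 30% | 40% |
|---|---|---|---|---|---|
| Average maximum dose | 1.00 | 1.00 | 1.00 | 1.00 | 1.00 |
| Mean dose per unit time | 1.00 | 1.10 | 1.20 | 1.30 | 1.40 |

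**Step 3: induction and maintenance mixed, on either reading.** Defining the maximum per unit time would bring frequency in, but a maximum still selects the most intensive phase. Treatment data cover 2 + 1 = 3 years. Inclusion criterion 2 requires a diagnosis at least two years before enrolment, so a biologic may have been started before the window opens, and its induction would then not be seen.

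Set maintenance to 1 and induction to k, measured on whichever reading applies. Let s be the share of courses whose induction falls inside the window. With both phases in one course:

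average maximum = s × k + (1 − s) × 1 = 1 + (k − 1)s

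| k (assumed) | s = 0 | s = 0.5 | s = 1 |
|---|---|---|---|
| 1 | 1.00 | 1.00 | 1.00 |
| 1.5 | 1.00 | 1.25 | 1.50 |
| 2 | 1.00 | 1.50 | 2.00 |
| 3 | 1.00 | 2.00 | 3.00 |

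Maintenance dosing is identical in every cell. The documents give neither k nor s, so the table shows a range and estimates nothing.

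**Step 4: what SAP 8.1.3 adds.** Three items bear on escalation. The failure outcome includes biologic dose escalation, which by the protocol 4.2 definition covers frequency, but pools it with switching, surgery and augmentation. Therapeutic escalation is recorded as present or absent by treat-to-target status. Dose modification is recorded as present or absent in each six-month period, without saying whether an interval change counts. None of the three reports a dose or an interval.

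**The case against.** The strongest reply is that the missing definition cuts both ways. SAP 8.1.2 never says that the maximum is per administration, so blindness to frequency is a reading, though the natural one. That stands, and Step 2 holds only on that reading. Steps 1 and 3 do not need it.

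A reader might infer that interval shortening is lost from the study. The documents do not support that: the SAP 8.1.3 items in Step 4 can register it. What is missing is a description of the dosing itself.

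A reader might also infer that the dosing table would show mainly the share of recent starters. That does not follow either. The effect in Step 3 depends on the drug, the ratio is assumed, and at k = 1 the effect is zero. SAP 8.1.2 does not label its statistic as maintenance dosing, and it leaves the term course undefined. Suppose the two phases count as separate courses, with one maintenance course per patient and s now the share of patients with induction in the window. The average over courses is then (sk + 1)/(s + 1). At k = 2 this is 1.33 for s = 0.5 and 1.50 for s = 1. The size changes, but the mixing remains.

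Protocol 15.2 promises a descriptive analysis of everything listed in its section 12, which includes the dosage regimen and the phase field. This is a fair point, but it names no dosing summary and does not tell the programmer what to produce. The SAP's example tables are not in the text available for review and may show more. Even so, the specification belongs in 8.1.2.

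**Conclusion.** The concern holds within SAP 8.1.2. Frequency, time on each dose regimen and treatment phase have no stated summary there, although SAP 6.1 puts the first two in the primary endpoint and the eCRF collects the third. This much rests on the documents alone.

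The numerical consequences are conditional. If dose means per administration, a halved interval is a 100% rise in dose per unit time and a 0% change in the statistic. If induction is more intensive than maintenance, the statistic is inflated by (k − 1)s relative to maintenance when both phases are in one course. That is between 0 and 100% at k = 2, and nothing at k = 1. The actual size cannot be derived from the documents.

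The study is descriptive, so no test or sample size is affected. This is a gap in how the primary endpoint is reported, and it is worth closing because the data are already collected.

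**What to change.** In SAP 8.1.2, for biologics:

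- Define the dose metric. Report dose together with interval, or equivalently dose per unit time.
- Report this, and the duration of each dose regimen, separately for induction and supportive care using the existing eCRF field, with the number of patients contributing to each phase.
- Report the number of patients with an increase in dose, in frequency, or in both.

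In SAP 8.1.3, state that a dose modification includes a change of interval, in line with protocol 4.2. Keep maximum daily dose for steroids, where it is collected.

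The cost is SAP wording and table programming. No new data are needed, and no clinical rule or sample size changes.

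### Average maximum dose is planned for immunosuppressant and 5-ASA components grouped by an undefined class with no common dose scale, so the average can shift with drug mix alone

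*SAP*

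**What the plan says.** SAP 8.1.2 lists 17 combinations (a to q) and introduces their summaries with "Each treatment combination will be analyzed using the following summary data". One of these is "Average maximum dose for each component of the combination (across all courses".

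The level of grouping differs by drug group within that list:

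- **Immunosuppressants:** by class, as in "Immunosuppressive monotherapy (by class". They appear in items b, c, d, h, i, k, m, p and q.
- **5-ASA:** by class, as in "5-aminosalicylic acid derivatives monotherapy (by class". They appear in items d and e.
- **TNF inhibitors:** by trade name, as in "TNF-alpha inhibitor monotherapy (by trade name". JAK inhibitors are handled the same way.
- **Vedolizumab:** by INN, as in "Vedolizumab monotherapy (by INN".
- **Steroids:** by class, with a footnote: "Steroids will be standardized through the calculation of prednisolone equivalent dose to facilitate comparisons between the classes".

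No similar footnote covers immunosuppressants or 5-ASA, and class is not defined for either.

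Protocol 12.6.1 names azathioprine, 6-mercaptopurine, methotrexate and cyclosporine A as immunosuppressants. Under "The following data should be documented for 5-ASA, immunosuppressive agents" it lists INN, route and daily dose among the items.

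**The concern.** A mean dose is interpretable when every value refers to the same drug, or when the values have been converted to a common scale. The steroid footnote shows that the SAP's authors recognised this for one group grouped by class. The other two such groups have no equivalent provision.

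If a class contains two molecules with different milligram doses, its average depends on how many patients take each one. Results are shown separately for UC and CD, and one combination is set beside another. If the drug mix differs between those columns, the averages will differ too, and a reader would naturally take that as heavier or lighter dosing. SAP 8.1.1 also attaches a 95% confidence interval to each mean, which would lend apparent precision to a number that describes no single drug.

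The summary sits in the section on the primary endpoint, and Protocol 6.2 makes the non-biological treatment regimen a primary outcome.

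**Working it through.** **Stated figure.** The documents give no value for average maximum dose, so there is nothing to reproduce. The check has two parts: what the text requires, and what follows arithmetically.

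**Reach.** Immunosuppressants occur in 9 of the 17 listed combinations. 5-ASA adds one more (item e, since d is already counted). So 10 of 17 combinations contain at least one component grouped by class without a common scale.

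**Model.** Take two drugs in one class. Let their mean maximum doses be 1 unit and k units, the same in every group of patients. Let s be the share of patients on the higher-milligram drug. Then

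class mean = (1 − s) + s·k

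The values of k and s are assumptions, because the documents give neither doses nor shares for these drugs. They serve only to show the arithmetic.

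| k | mean at s = 0.3 | mean at s = 0.7 | ratio |
|---|---|---|---|
| 1 | 1.00 | 1.00 | 1.00 |
| 1.5 | 1.15 | 1.35 | 1.17 |
| 2 | 1.30 | 1.70 | 1.31 |
| 5 | 2.20 | 3.80 | 1.73 |
| 10 | 3.70 | 7.30 | 1.97 |

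For example, at k = 5: 0.7 + 0.3 × 5 = 2.2 and 0.3 + 0.7 × 5 = 3.8, and 3.8 / 2.2 = 1.73.

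**Bounds.** Only k = 1 leaves the mean unchanged. As k grows, the ratio for a shift from 30% to 70% approaches 0.7 / 0.3 = 2.33 and cannot exceed it.

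**Interpretability.** At k = 5 and s = 0.5 the mean is 0.5 + 0.5 × 5 = 3.0 units, a dose typical of neither drug. The between-drug standard deviation alone is 0.5 × (5 − 1) = 2.0 units.

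**Median.** The median that SAP 8.1.1 already requires does not help if it is taken over the pooled class. With each drug at one fixed dose, the pooled median is 1 at s = 0.3 and k at s = 0.7.

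**After the change.** Reported per drug, each mean stays at 1 or k whatever the mix, so the artificial ratio is 1.00 in every row.

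**The case against.** The strongest reply is that by class may mean a breakdown into classes of immunosuppressant, just as by trade name means a breakdown into products. The steroid footnote speaks of several classes within steroids, which supports that reading. It stands in part. A reader might infer that all four immunosuppressants are averaged together, and the documents do not say so. Sub-classes would narrow the mixing, but it disappears only if class means a single drug, and the SAP uses different terms where it means that.

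The example tables in SAP 9.1 were not in the text available for this review. The SAP's history of changes says they were re-worked when maximum dose was added, so a per-drug row there cannot be excluded. The point therefore rests on the wording of 8.1.2.

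Several stronger readings are tempting but unsupported:

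- **A conflict with SAP 6.1.** Its request for dose, route and frequency belongs to the endpoint for patients on biologics. It is not a requirement on immunosuppressants or 5-ASA.
- **Distorted regional comparisons.** In SAP 8.1.2, region belongs to the distribution of patterns, a separate item from maximum dose. SAP 7.4 has no region subgroup.
- **A several-fold distortion.** That needs a more extreme swing in drug mix than 30% to 70%, combined with a large dose ratio. The documents support neither.
- **A missing dosing-interval field.** The eCRF is not in the documents, and nothing in them says that a listed immunosuppressant is given other than daily. A new field would also come after the end of data collection planned in Protocol 10.2 (Q3–Q4 2021), since this SAP version is dated 30.12.2021.

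It is also fair to say that the impact is small. The SAP's own primary endpoint is worded for biologics, whose doses are kept by trade name or INN.

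**Conclusion.** The point holds in a limited form. Followed as written, SAP 8.1.2 gives a mean that depends on drug mix for any immunosuppressant or 5-ASA class containing more than one molecule with different milligram doses. For a shift in share from 30% to 70%, the size is 1.17-fold to 1.97-fold under assumed dose ratios of 1.5 to 10. The factor depends on those assumptions, but the existence of the effect requires only unequal doses and unequal mix.

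Comparisons of average maximum dose between UC and CD, or between combinations, are exposed. The effect does not touch any test, the sample size, the counts of combinations, or the dose summaries of TNF inhibitors, JAK inhibitors and vedolizumab. In combinations that pair one of those with an immunosuppressant, only the immunosuppressant component is affected. A reader should not conclude that the primary results as a whole are unsound. This is a cheap improvement to one descriptive summary.

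**What to change.** In SAP 8.1.2:

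1. For immunosuppressants and 5-ASA, replace the class-level average maximum dose with maximum dose by INN and route, showing n, unit, median and quartiles.
2. Define class for both groups and use it only to count combinations.
3. Make the example tables in SAP 9.1 match, if they do not already.

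No new data are needed, since Protocol 12.6.1 already records INN and route. The cost is more table rows and small numbers for rarely used drugs, which showing n makes visible.

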11.1 Inclusion Criteria

Every eligible patient at participating investigational sites must meet the following criteria:

Inclusion criteria:

1. Male and female patients 18 years or older by the time of enrolment
2. Confirmed diagnosis of Crohn's disease or ulcerative colitis for at least 2 years prior to enrolment in the study.
3. The presence of a moderate to severe IBD flare at the time of enrolment or in patient anamnesis within 2 years before enrollment treated with steroids or/ and immunosuppressive agents or/ and biologic therapy. IBD flare(s) must be confirmed in the source documentation.
4. Current treatment with steroids or/ and immunosuppressive agents or/ and 5-ASA or/ and biologic therapy
5. Written informed consent, signed before the participation in the study begins.

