## 5.3 Study stages and procedures

Due to the non-interventional study design it's not possible to appoint exact times for the study visits, although it is expected that the period of observation will be approximately 12 months. The frequency of the visits will be assigned by each physician according to their routine practice. It is anticipated that the patients will visit their physician 2 times after enrolment into the study, i.e., approximately every 6 months ( $\pm$  30 days). Information for the study will be collected from 3 visits:

- Visit 1 (Baseline visit, V1) - study enrolment and retrospective data collection;
- Visit 2 (Observational visit, V2) - 6 months ( $\pm$  2 weeks) after study enrolment;
- Visit 3 (Final observational visit, V3) - 12 months ( $\pm$  2 weeks) after study enrolment.

Tabulated overview of visits and procedures performed on these visits is provided in the following table.

Protocol ID	MACS -2017-102279	STATISTICAL ANALYSIS PLAN	Page 10 of 41	
IP	N/A		Date	30.12.2021
ID	MACS -2017-102279_SAP		Version	v1.2 final

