#### 8.1.3 Assessment of secondary and exploratory endpoints

**Each original treatment combination** (defined as the treatment combination that was used by the patient at the very start of retrospective observation period, i.e. first recorded treatment combination in the study) will be tabulated by the below listed parameters using the generic table format below (see example tables: Table 10, Table 11, Table 12 and Table 6):

- Demographic data;
- Disease activity at Visits 1, 2, 3 (Mayo, Harvey-Bradshaw indices);
- Disease status assessed by investigator at Visits 1, 2, 3;
- Frequency (percentage) of clinical, endoscopic and histologic remission at Visits 1, 2, 3 and retrospective period of observation;
- Extent of lesion at Visits 1, 2, 3;
- Systemic (extraintestinal) manifestations at Visits 1, 2, 3;
- Total number, duration and severity of disease exacerbations by Visit 1, 2 and 3;
- Total number, type and duration of disease complications by Visit 1, 2 and 3;
- Laboratory and instrumental assessments at Visits 1, 2, 3;
- Percentage of patient with surgical treatment by Visits 1, 2, 3 grouped by:
  - Indication;
  - Surgery type;
  - Presence of complications.
- Number of surgeries by Visits 1, 2, 3;

Protocol ID	MACS-2017-102279	STATISTICAL ANALYSIS PLAN	Page 25 of 41	
IP	N/A		Date	30.12.2021
ID	MACS-2017-102279_SAP		Version	v1.2 final

- Percentage of patients with at least one episode of failure or biological or/and non-biological therapy (e.g., dose escalation of biologics, switching to another therapy, IBD-related surgery, medication augmentation) by Visits 1, 2 and 3;
- Separately for patients who achieved / not achieved T2T treatment goals (based on the clinical assessment of IBD) by Visits 1, 2 and 3:
  - Presence of therapeutic de-escalation;
  - Presence of therapeutic escalation;
  - Continuation of therapy without any changes.
- Healthcare resources utilization:
  - Hospitalizations due to complications;
  - IBD-related surgeries;
  - Percentage of patients that used healthcare resources;
- Only for biological therapy - percentage (by Visits 1, 2, 3) of patients with:
  - Positive test results for TB before the start of biological therapy;
  - Active TB before the start of biological therapy;
- Percentage of patients by Visits 1, 2, 3 with:
  - Reactivation of TB;
  - New occurrence of TB.

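### SAP 8.1.2 breaks treatment patterns down by Visit 1 disease activity, which for any course begun before enrolment is measured after treatment started

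*SAP*

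**What the plan says.** SAP 6.1 sets the window of the primary endpoint: "Treatment patterns will be evaluated within 2 years before enrolment – retrospective data and one year after enrolment". SAP 8.1.2 says what is counted: "Treatment pattern will include unique combination of certain treatments or treatment combinations along with their change over time". One of its summaries pools the two periods: "Total duration of use of each combination / course for the total duration of observation (retro- and prospective". The last summary in that list is "Distribution of each pattern by subgroups: age, gender, region, duration of the disease, disease activity (according to Visit 1 Mayo / Harvey-Bradshaw indices". Neither a period nor a course start date is attached to the activity subgroup.

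SAP 5.3 places the score in time: "Visit 1 (Baseline visit, V1) - study enrolment and retrospective data collection". The visit schedule (SAP Table 1, Protocol 12.2) marks disease activity data at Visits 1, 2 and 3, with no mark under retrospective collection.

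Protocol 11.1, criterion 3, admits a patient on "The presence of a moderate to severe IBD flare at the time of enrolment or in patient anamnesis within 2 years before enrollment", provided the flare was treated with steroids, immunosuppressives or biologics. Criterion 4 requires that the patient is on IBD treatment at enrolment.

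Two other SAP sections handle activity differently. SAP 8.1.3 reports Visit 1 activity as a later status, tabulated by the first combination on record. SAP 7.4 groups first-line vedolizumab, ustekinumab, anti-TNF and tofacitinib by activity when the drug was prescribed.

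**The concern.** Age, gender, region and disease duration describe the patient whatever drug was given. A Mayo or Harvey-Bradshaw score does not, once treatment has started. Placing the Visit 1 score in the same list invites the reader to treat it as the same kind of variable.

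The eligibility rules make this more than a technicality. A patient in remission at Visit 1 is not flaring, so can have qualified only through an earlier, treated flare. The low-activity stratum therefore holds patients whose disease has improved since that flare. Their score does not describe the disease for which the earlier treatment was chosen.

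The primary objective is to describe which treatments are used in moderate to severe disease. A table of patterns by activity will be read as showing who receives what. For courses begun before enrolment it shows a mixture of choice and response, and a reader could not separate the two afterwards.

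**Working it through.** **1. The plan's own figure.** The plan gives no figure for this table. Its one design figure (Protocol 15.4) is the precision for Crohn's disease patients on biologics. It reproduces: n = 2000 × 0.40 × 0.40 × 0.90 = 288; half-width = 1.96 × √(0.5 × 0.5 / 288) = 5.77 points, giving 44.2% to 55.8%. It is not in dispute, and nothing below changes the sample size.

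**2. Where Visit 1 falls in the window.** From SAP 6.1 and 5.3, the nominal share of the window before Visit 1 is 24 / (24 + 12) = 66.7%. It is 24 / 30 = 80% for a patient who leaves at month 6, and 12 / 24 = 50% for one with only 12 months of records and full follow-up. These are shares of window time. The documents do not say how many courses or patterns lie before Visit 1.

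**3. What the Visit 1 score means for each kind of course.**

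| Course | Visit 1 score relative to course start | Meaning |
|---|---|---|
| Ended before Visit 1 | After | Status after treatment |
| Started before, running at Visit 1 | After | Status on treatment |
| Started on or after Visit 1 | Not after | Patient descriptor |

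Because criterion 4 requires current treatment, the second row matters. A drug carried from before enrolment into the first six months of follow-up has the same reversed order, although the period is prospective.

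**4. Illustration of how far the table can move.** The biologic share b = 40% is the assumption in Protocol 15.4. Everyone is assumed equally active at course start. The remission rates by Visit 1, r_B on biologics and r_N on non-biologics, are assumptions; the documents give none.

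- Biologic share of the remission stratum = b·r_B / [b·r_B + (1 − b)·r_N]
- Biologic share of the active stratum = b(1 − r_B) / [b(1 − r_B) + (1 − b)(1 − r_N)]

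For r_B = 60% and r_N = 30%: 0.24 / (0.24 + 0.18) = 57.1%, and 0.16 / (0.16 + 0.42) = 27.6%.

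| r_B | r_N | Biologic share, remission at Visit 1 | Biologic share, active at Visit 1 |
|---|---|---|---|
| 30% | 30% | 40.0% | 40.0% |
| 40% | 30% | 47.1% | 36.4% |
| 50% | 30% | 52.6% | 32.3% |
| 60% | 30% | 57.1% | 27.6% |
| 30% | 40% | 33.3% | 43.8% |
| 30% | 60% | 25.0% | 53.8% |

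If activity were taken at course start, every patient in this example would fall in one stratum with a biologic share of 40%. The departures from 40% are entirely response, and their sign follows the assumed rates.

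**5. The 2019 interim analysis.** SAP 8.7 applies the 8.1.2 method to the two retrospective years alone. There the treatment history precedes the Visit 1 score throughout.

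**The case against.** The strongest case for leaving the text alone has five parts.

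- **The line is openly labelled and small.** It names Visit 1, activity is one of five subgroup variables, and no sentence says that it is activity at the time of choice. This stands as far as scope goes: the distribution of patterns does not depend on the Visit 1 score. It does not settle how the table will be read, since the other four variables in the list are patient characteristics.
- **The analysis is descriptive.** SAP 8.1.1 plans no test of the primary endpoint, and Protocol 15.2.4 concedes that effectiveness cannot be fully evaluated. Both are true and limit the weight of the point. A descriptive table must still say what it describes.
- **Other sections already help.** SAP 7.4 uses activity at prescription, and SAP 8.1.3 splits patterns into periods and reports "Total number, duration and severity of disease exacerbations by Visit 1, 2 and 3". But 7.4 does this only for the first-line subgroups, the schedule marks no retrospective score to supply it, and 8.1.3 does not tie the activity subgroup to a period.
- **Flare severity is a poor substitute.** Criterion 3 already requires a moderate to severe flare, so the scale is truncated. Severity follows national guidance and local practice (Protocol 4.2), not one defined scale, and some courses, such as maintenance 5-ASA, may have no flare at their start. This stands: flare severity can supplement the table but not carry it.
- **The size is hypothetical.** This stands too. Patients who differ in severity may be given different drugs, which could shrink, cancel or reverse the contrast, and the share of patients flaring at enrolment is unknown.

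**Conclusion.** The point holds within limits. For any course started before Visit 1, SAP 8.1.2 uses as a subgroup variable a score measured after treatment began, and nothing in that section restricts or relabels it. The time order follows from the documents alone. The size and direction of the distortion do not: the illustration rests on assumed remission rates, equal starting activity and the plan's 40% biologic share.

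A reader might infer three stronger things that the documents do not support:

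- That two thirds of the patterns precede enrolment. The 67% is nominal window time, and a pattern can span Visit 1.
- That effective drugs will appear to be given to patients with mild disease. The sign depends on rates that the documents do not give.
- That the primary result is biased, or that every prospective pattern is free of the problem. The overall distribution is untouched, while courses continuing through Visit 1 share the fault.

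The consequence is confined to one descriptive subgroup table and to its use in the 2019 retrospective interim analysis. It should be corrected because the correction is cheap and changes what that table shows.

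**What to change.** In SAP 8.1.2:

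1. Use Visit 1 Mayo or Harvey-Bradshaw score as a patient descriptor only for courses started on or after Visit 1. Start dates are already collected (Protocol 12.6.1), so the rule can be applied course by course, including within a pattern that spans Visit 1.
2. For courses started earlier, report the same score under a label such as *status at enrolment, on or after treatment*, and not as a characteristic of who received the pattern. Apply the label to any 2019 interim table that is reused.
3. Where a dated, source-documented flare at or before course start is available, add its severity as a supplementary breakdown and show the number missing. This agrees with the prescription-time anchor in SAP 7.4.

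Steps 1 and 2 need wording and table shells only: no new data and no change in sample size. The cost is fewer courses in the Visit 1 activity breakdown. Step 3 depends on confirming that dated flare severity was captured. It will be incomplete and coarse, because criterion 3 already requires a moderate to severe flare.
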